biopsy needles directly inserted through the perineal skin rather than bowel, the risk of sepsis is reduced. However, this technique requires multiple needles traversing through the perineum, and requires to be carried out under general anaesthesia (GA). Another disadvantage is a stabilising stepping unit is required to provide a consistent alignment of the ultrasound probe against the prostate in order to carry out the biopsies. Such stabilising stepping units are costly.

A novel but simple transperineal access system device known as PrecisionPoint (Perineologic, Cumberland, MD, USA) has been developed to tackle the aforementioned limitations of TPB. This revolutionary device utilises a single access needle cannula mounted directly on to the ultrasound probe, which acts as an access point traversing through the perineal skin. This design minimises the number of needle punctures through the skin, enabling TPB to be carried out under LA. A stabilising stepping unit is not required with this technique. The device has gained the United States Food and Drug Administration (FDA) approval [11], and results from small contemporary series have already been published with very promising results in terms of cancer detection rate and safety [12].

TRUSB has a poor cancer detection rate and is associated with potentially fatal septic risk. TPB, if able to be carried out under LA as an office-based procedure, can potentially provide a better cancer detection rate with significantly reduced sepsis risk. It has fundamentally a very high potential to become the new gold standard in obtaining prostate tissue for histological diagnosis of PCa.

With an increasing number of men in Hong Kong with elevated serum PSA suspicion of PCa needing prostate biopsy, we strongly feel that it is fundamental to carry out a study to determine the most effective, safe and tolerable prostate biopsy technique which fits with the clinical practice in Hong Kong.

Aim of study

To evaluate whether TPB using a noval transperineal access system under LA is superior to standard 12-cores TRUSB in detecting prostate cancer (PCa), in patients with clinical suspicion of PCa with no prior prostate biopsy.

Other objectives of the study include:

- > To assess whether LA TPB has reduced post-biopsy sepsis rate
- To assess whether patient tolerability with LA TPB is non-inferior to standard TRUSB

Study design and method

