Patient recruitment and enrollment will take place at urology outpatient clinics at a tertiary university teaching hospital. In 2017, on average 16 biopsy-naïve men with raised serum PSA underwent TRUSB per month. It is therefore estimated that the study will complete within 26 months of commencement. The start date of the study will be 1st April 2019, and the estimated completion date for recruitment will be 1st June 2021.

Statistical analysis

Primary outcome analysis will be based on intention to treat sample as well as per protocol sample.

Primary endpoint is difference in proportion of patients with PCa detected between the two cohorts based on histopathological analysis. Absolute differences in PCa detection rate will be calculated with 95% CIs. If lower bound of 97.5% CI for the difference in cancer detection rates of LA TP biopsy compared with TRUS biopsy is greater than -5%, then TP biopsy will be deemed non-inferior. If lower bound is greater than 0, TP will be deemed superior. Comparisons will be made concerning the basic characteristics between the two arms of participants. If any imbalance were identified, a multivariable logistic regression analysis will be carried out, with clinically significant PCa as the dependent variable and group as the independent variable. Any baseline characteristics imbalance will be used as a covariate.

Effect sizes concerning secondary outcomes will be presented with 95% CIs. For binary outcomes, differences between the two arms will be calculated with 95% CIs. Any imbalance between the two arms will again be accounted for with a multivariable logistic regression analysis. For continuous outcomes, mean differences in outcomes between the two study arms will be calculated with 95% CIs. Imbalances identified between the two groups will be accounted for in a multivariable linear regression analysis. Non-parametric test will be used if any secondary outcomes were found not normally distributed. All statistical analysis will be carried out using the SPSS software.

Primary end-point

Primary outcome is proportion of participants identified with PCa, assessed on a per patient basis from each individual's biopsy histopathological analysis report (i.e. comparison of absolute cancer detection rate). Definition of PCa is presence of any PCa regardless of grade on histopathology. Definition of clinically significant PCa is any core containing Gleason grade 3+4 disease or above. Timeframe for

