assessment will be when histopathology reports are available, usually expected to be within 14 days following biopsy procedures.

Secondary end-points

Secondary outcomes, tools for assessment, and their corresponding timeframe for assessment are summarized in table below.

Secondary outcomes	Assessment tool	Timeframe for
	(if applicable)	assessment
Procedure tolerability	Visual Analogue	Immediately following
	Scale (VAS)	test
Health-related quality of	EQ-5D-5L	Baseline, 24 hours post-
life and patient	questionnaire,	biopsy, and 30 days
satisfaction	IPSS, IIEF	post-biopsy
Proportion of men	Either:	1 week to 30 days post-
developing sepsis	1) admission to	biopsy
	hospital for	
	urosepsis; or	
	2) Presence of	
	rittines in unne at	
Detection rates of	Histopathology	When histonathology
natients with clinically	report	results available
significant PCa (Gleason		expected to be within 14
3+4 or higher)		days following biopsy
Maximum cancer core	Histopathology	When histopathology
length (MCCL, mm)	report	results available,
3 (, , ,		expected to be within 14
		days following biopsy
Proportion of men go on	Clinical records,	After treatment
to undergo definitive	patient interview	decision, expected to be
curative treatment for		within 30 days following
local disease (including		biopsy
surgery and		
radiotherapy)		
Procedure times	Time from start of	During test
(minutes)	ultrasound probe	
	insertion to probe	
Cost por diagnosis of		20 dava post biopay
cost per ulagriosis Of		ou days post-biopsy

Data Access and Handling

To protect patient privacy, all research data will be handled in line with Hospital Authority's or Hospital's policy in handling/storage/destruction of patients' medical records. They would be locked in cabinets where the department/ward keep patients' medical records. Electronic data would be saved in secured computer of the hospital with restricted access. USB Device would not be used for patient information for personal data.

Personal data (name, HKID, address and any other personal identifiable information) will not be recorded on the projects' data sheets or electronic files. A study code will be used.

Any documents or electronic files containing personal identifiable information would be considered as part of the medical record and will be dealt with the same stringent regulations of security according to the hospital policies. The principal investigator/co-investigator will be responsible for the execution of data protection.

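### Maximum cancer core length falls under the general mean-difference rule although it is measurable only in men with detected cancer, so the comparison is not protected by randomisation and can be biased in either direction

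*Protocol*

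**What the plan says.** The table under *Secondary end-points* in the Protocol has a row for "Maximum cancer core" "length (MCCL, mm"), with the histopathology report as its source. The row names no analysis population and does not say how a man without cancer is scored.

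The *Statistical analysis* section treats all continuous outcomes alike:

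- Effect measure: "For continuous outcomes, mean differences in outcomes between the two study arms will be calculated with 95% CIs".
- Adjustment: "Imbalances identified between the two groups will be accounted for in a multivariable linear regression analysis".
- Fallback: "Non-parametric test will be used if any secondary outcomes were found not normally distributed".

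No exception is made for MCCL. Intention-to-treat and per-protocol samples are named for the primary outcome only.

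Under *Primary end-point*, "Primary outcome is proportion of participants identified with PCa", and "Definition of PCa is presence of any PCa regardless of grade on histopathology". *Aim of study* asks whether TPB "is superior to standard 12-cores TRUSB in detecting prostate cancer (PCa").

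**The concern.** A core has a cancer length only if it contains cancer. Whether any core does is the primary outcome, and the trial's hypothesis is that this differs by arm. The men with an MCCL in one arm are therefore not the counterparts of the men with an MCCL in the other. Randomisation balances the full arms. It does not balance subsets defined by what the biopsy technique found.

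Neither stated safeguard addresses this. Regression on baseline imbalances deals with chance differences between the randomised groups, whereas here the difference arises from detection after randomisation. A non-parametric test changes the statistic but not who contributes a value.

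At stake is a misleading secondary result. The trial could report a difference in cancer length, for or against TPB, when both techniques measure the same length in every cancer that both would find.

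**Working it through.** **No Protocol figure to reproduce.** The Protocol gives no expected MCCL mean, SD, detection rate or power for this endpoint. Everything below except the arm size is an assumption.

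**Inputs**

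- Men per arm: n = 165 (Protocol, sample-size paragraph under *Study design and method*).
- TRUSB detection rate: p = 0.30 (assumed; 0.25 to 0.40 in the range below).
- Extra detection by TPB: d = 0.10 (assumed; 0.05 to 0.15 in the range below).
- Mean MCCL of cancers that either technique finds: m = 6 mm, identical in both arms (assumed).
- Mean MCCL of the extra cancers found only by TPB: s = 3, 6 or 8 mm (assumed; the Protocol does not say whether they are shorter or longer).

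**Men who would have an MCCL.** TRUSB: 165 × 0.30 = 49.5. TPB: 165 × 0.40 = 66.

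**Difference among cancer-positive men (TPB minus TRUSB)**

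(p·m + d·s)/(p + d) − m = d·(s − m)/(p + d)

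| s | TPB mean among positives | Difference |
|---|---|---|
| 3 mm | (0.30 × 6 + 0.10 × 3)/0.40 = 5.25 mm | -0.75 mm |
| 6 mm | (0.30 × 6 + 0.10 × 6)/0.40 = 6.00 mm | 0 |
| 8 mm | (0.30 × 6 + 0.10 × 8)/0.40 = 6.50 mm | +0.50 mm |

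The sign is that of s − m. In every row, the techniques do equally well on the cancers both find.

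**Range for p = 0.25 to 0.40 and d = 0.05 to 0.15**

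- s = 3 mm: from 0.05 × (−3)/0.45 = -0.33 to 0.15 × (−3)/0.40 = -1.125 mm.
- s = 8 mm: from 0.05 × 2/0.45 = +0.22 to 0.15 × 2/0.40 = +0.75 mm.

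**How often it would reach significance.** Assume also that the SD is half the mean: 3 mm for the shared cancers, and 1.5 mm or 4 mm for extra cancers averaging 3 mm or 8 mm. With p = 0.30 and d = 0.10, a quarter of TPB positives are extra cancers.

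- s = 3 mm: TPB variance = 0.75 × 9 + 0.25 × 2.25 + 0.75 × 0.25 × 3² = 9.0. SE = √(9/49.5 + 9/66) = 0.564. The ratio is −0.75/0.564 = −1.33, so about 26% of trials would show a significant result against TPB.
- s = 8 mm: TPB variance = 0.75 × 9 + 0.25 × 16 + 0.75 × 0.25 × 2² = 11.5. SE = √(9/49.5 + 11.5/66) = 0.597. The ratio is 0.50/0.597 = 0.84, so about 13% would show a significant result in favour of TPB.
- s = 6 mm: about 2.5% in each direction, the nominal level.

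Simulating 4,000 trials with gamma-distributed lengths and an unequal-variance t test gave 25% against TPB at 3 mm and 13% in favour at 8 mm. A rank test on the same data gave 31% and 10%, so the fallback does not remove the bias. The rates depend on the assumed SD: with an SD of 4 mm for the shared cancers, the 3 mm case falls to about 16%.

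**All men, 0 mm where no cancer is found.** The difference is (p·m + d·s) − p·m = d·s, which is +0.3, +0.6 and +0.8 mm for s = 3, 6 and 8 mm. At s = 3 mm the two choices of population give opposite signs on the same data (-0.75 and +0.3 mm).

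**The case against.** **The restriction to cancer-positive men is inferred.** The Protocol never says that cancer-free men are left out, and its rule speaks of the two study arms. Read literally, that could mean everyone. An analysis plan, which is not at hand, might define the population and the scoring of negative men, and such detail is often left there. This stands as far as it goes: a reader might infer that the Protocol prescribes a comparison of positives only, and it does not. But a cancer length has no natural value in a man without cancer, so reported lengths come from positives. The Protocol does fix a mean difference for every continuous outcome, and the objection is to applying that rule to this variable.

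**The direction is not given.** A reader might infer that TPB will look worse because its extra cancers are small. The documents do not support that. The background text says that TRUSB misses many tumours in the anterior and apical regions, and that over 30% of men with low-risk cancer on TRUSB harbour clinically significant disease. Longer extra cancers, and a bias flattering TPB, are equally plausible. This stands in full, and no single significance rate should be taken as a forecast.

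**Little rests on MCCL.** It has no hypothesis, margin or success rule and does not appear among the aims. Detection of clinically significant cancer, which can be compared over whole arms, is already a secondary endpoint. This also stands and sets the weight of the point.

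**Scoring 0 mm is a choice of estimand.** The all-men mean partly restates the detection difference and gives data with many zeros. For that reason it is offered only as an option.

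**Conclusion.** The point holds in a limited form. The general mean-difference rule does not suit MCCL: applied to reported lengths, it compares groups selected by the primary outcome, and neither the baseline regression nor a rank test repairs that. Under the assumed inputs the spurious difference is -0.75 mm, 0 or +0.5 mm according to whether the extra TPB cancers average 3, 6 or 8 mm.

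The sizes rest wholly on assumed detection rates and lengths, and on equal lengths in both arms for the shared cancers. The lack of protection by randomisation does not depend on those figures. The documents do not establish that the bias runs against TPB, or that cancer-free men will in fact be excluded. The point is minor, because MCCL is one of several secondary endpoints and no decision depends on it.

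**What to change.** Add a short exception to the continuous-outcome rule in *Statistical analysis*:

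- Report MCCL among cancer-positive men descriptively by arm. State that this is not a randomised comparison and supports no between-arm test or superiority claim.
- Optionally, if a randomised comparison is wanted, make it over all randomised men with a biopsy result, with 0 mm where no cancer is found. Use a bootstrap 95% CI for the mean difference or a rank-based method, and note that the result mixes detection with length. Report by arm how many randomised men have no biopsy result.

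This takes a few sentences and no new data. The price is that there is no formal test of MCCL among cancer-positive men. The optional analysis is also less familiar to clinicians than a mean length among positives, which the descriptive table still supplies.
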